**3.3. MTD Definition**

The estimated MTD is the dose level associated with approximately 27.5% of DLT-evaluable patients experiencing a DLT. The target interval for the DLT rate is (22.5%, 32.5%) Due to the discreteness of the dose levels and in the interest of the safety of the patients, the estimated MTD is the highest tested dose level with DLT rate  $\leq$ 32.5% (see [Table 2](#)).

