### 3. STUDY DESIGN

#### 3.1. Study Overview

[figure not shown]
This is a Phase 1, open-label, multi-center, multiple-dose, safety, PK and PD study of single agent PF-06840003. This study contains two parts, dose escalation (Part 1) followed by dose expansion (Part 2). In Part 1, sequential cohorts of patients with recurrent malignant gliomas (GBM and/or WHO grade III anaplastic gliomas) will receive escalating doses of PF-06840003. Part 2 will evaluate safety as well as explore preliminary antitumor activity of the dose selected from Part 1 in additional patients with GBM.

The actual number of patients enrolled in the study will depend on the tolerability of PF-06840003 and the number of dose levels required to identify the MTD or Recommended Phase 2 Dose (RP2D) if the MTD is not reached. The target sample size for each cohort in Part 1 is 2-4 patients, but, the actual number of patients treated at each dose will vary from 2 to 12. It is estimated that the maximum sample size will be approximately 72 patients in Part 1 of the study, although this may be higher if more than 6 dose levels are required to be evaluated. Up to approximately 20 to 25 patients are anticipated to be enrolled in Part 2 of the study.

PF-06840003 will be administered daily as an oral dose in 28 day cycles with a starting dose of 125 mg once daily (QD). The pre-specified nominal doses for use in the dose escalation are 125 mg/day, 250 mg/day and 500 mg/day of PF-06840003. If the MTD or RP2D are not reached within the pre-planned nominal dose range, and the PK and PD data show that the target coverage is not optimal, the sponsor, in conjunction with the investigators, after careful consideration of all available safety, laboratory and PK information may expand the nominal dose range to a higher dosage, up to a maximum dosage of 1000 mg per day. Based on emerging clinical and PK data, twice a day (BID) dosing may be explored. For example, if the exposure over 24 hours does not allow for sufficient target coverage it may be determined that BID dosing is needed. In such a case, BID dosing will be initiated at the QD dose level where no DLTs are observed (ie, starting dose of BID dosing will be 250 mg BID after safety and tolerability profile of 250 mg QD is confirmed). Once a BID dosing regimen is initiated for further escalation towards the MTD, the escalation with a QD regimen will be suspended. Intermediate doses may also be used if required.

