**Table 1. Dose Escalation Potential Dose Levels**

| Potential Dose Level | PF-06840003 (mg QD)*  | PF-06840003 (mg BID)  |
|----------------------|---|---|
| Starting Dose        | 125   | N/A   |
| 2                    | 250   | N/A   |
| 3                    | 500   | 250   |
| 4                    | 750   | 500   |
| 5                    | 1000  | 750   |
| 6                    | To be determined  | 1000  |
| 7                    | Escalation to continue to the MTD or desired pharmacological activity | Escalation to continue to MTD or desired pharmacological activity |

\* While a more frequent dosing regimen is initiated for further escalation towards the MTD, the escalation with a QD regimen will be suspended.

The mTPI method relies upon a statistical probability algorithm, calculated using all patients treated in the current dose level to determine one of the following dose-finding decisions: the subsequent dose should be escalated, maintained at the current dose, or de-escalated in the next cohort of 2 to 4 patients, or the trial should be terminated.

As an example, if the total number of patients treated at the current dose level is 4, the following dosing rules are applied:

- 0 DLT -> escalate
- 1 DLT -> remain at the same dose
- 2 DLTs -> de-escalate
- 3-4 DLTs -> de-escalate and consider current dose as intolerable

The general approach to dose-finding, using the mTPI method, involves the following:

- The target cohort size is 2 to 4, depending on the number of potential patients identified at participating sites;
- The next cohort can be enrolled when all patients at the current dose cohort have been evaluated for 28 days of the first treatment cycle, or experience a dose-limiting toxicity (DLT), whichever comes first;
- If a patient withdraws from the study before receiving  $\geq 80\%$  of the planned first-cycle dose for reasons other than investigational product-related toxicity, another patient will be enrolled to replace that patient at the current dose combination;
- In the situation in which the safety of the starting dose does not allow for escalation to the next dose level, a lower dose will be considered.

The dose escalation portion of the study is completed when at least 6 to 12 evaluable patients have been treated at the highest dose associated with DLT rate  $\leq 32.5\%$ .

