**Table 2. Decision Rules**

| Number of Patients having DLT | Number of Patients Treated at a Dose Level |     |     |     |     |     |     |     |      |      |      |
|-------------------------------|--|-----|-----|-----|-----|-----|-----|-----|------|------|------|
|                               | n=2  | n=3 | n=4 | n=5 | n=6 | n=7 | n=8 | n=9 | n=10 | n=11 | n=12 |
| 0                             | E  | E   | E   | E   | E   | E   | E   | E   | E    | E    | E    |
| 1                             | S  | S   | S   | E   | E   | E   | E   | E   | E    | E    | E    |
| 2                             | U  | D   | S   | S   | S   | S   | S   | S   | S    | E    | E    |
| 3                             |  | U   | U   | D   | D   | S   | S   | S   | S    | S    | S    |
| 4                             |  |     | U   | U   | U   | U   | D   | D   | D    | S    | S    |
| 5                             |  |     |     | U   | U   | U   | U   | U   | D    | D    | D    |
| 6                             |  |     |     |     | U   | U   | U   | U   | U    | U    | U    |
| 7                             |  |     |     |     |     | U   | U   | U   | U    | U    | U    |

Actions to be taken:

D = De-escalate the dose; E: Escalate the dose; S: Stay at the dose.

U = Unacceptable toxicity.

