## **9.2. Statistical Methods and Properties**

### **9.2.1. Statistical Methods for Dose Escalation/De-Escalation**

Part 1, the dose escalation phase of this study, employs an mTPI design to estimate the MTD. The mTPI design employs a simple beta binomial model with a conjugated prior beta (0.5, 0.5). Decision rules are based on calculating the unit probability mass (UPM) of 3 intervals corresponding to underdosing, proper dosing, and overdosing in terms of dose limiting toxicity. A proper dosing interval is centered at the target toxicity rate (pT) of 27.5% with 5% uncertainty ( $0.225 < pT < 0.325$ ). The under dosing interval is (0, 0.225), and the overdosing interval is (0.325, 1). The 3 dosing intervals are associated with 3 different dose escalation decisions. The underdosing interval corresponds to a dose escalation I, overdosing corresponds to a dose de-escalation, and proper dosing corresponds to staying at the same current dose. Given an interval and a probability distribution, the UPM of that interval is defined as the probability of the interval divided by the length of the interval. The mTPI design calculates the UPMs for the 3 dosing intervals, and the one with the largest UPM implies the corresponding dose finding decision. That decision provides the dose level to be used for future patients. For example, if the underdosing interval has the largest UPM, decision E (to escalate) will be executed, and the next cohort of patients will be treated at the next higher dose level. Under the mTPI design, a trial is terminated when either the lowest dose is above the MTD or a pre-specified maximum sample size is reached. Doses with an incidence of DLT >33% (eg, 4 out of 10) will not be declared as MTD even though it is allowed by the mTPI method.

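### Section 3.3's MTD rule can name a well-tolerated top dose as the MTD while Table 2 still says to escalate

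*Protocol*

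**What the plan says.** Section 3.3 first describes the target: "The estimated MTD is the dose level associated with approximately 27.5% of DLT-evaluable patients experiencing a DLT", with a target interval of 22.5% to 32.5%. Its last sentence then gives the working rule. Citing the discreteness of the dose levels and patient safety, it states that "the estimated MTD is the highest tested dose level with DLT rate" at or below 32.5%, and it points the reader to Table 2.

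Other text bears on the same decision:

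- Table 2 (repeated in SAP Section 4.2) assigns Escalate, Stay, De-escalate or Unacceptable to each DLT count for 2 to 12 patients.
- Section 3.1.1 completes escalation once at least 6 to 12 evaluable patients have been treated at the highest dose meeting the same 32.5% limit.
- Section 9.2.1 and SAP Section 8.1 add one exclusion: a dose with more than 33% DLTs "will not be declared as MTD even though it is allowed by the mTPI method".
- Table 1 ends its QD column with "Escalation to continue to the MTD or desired pharmacological activity". Section 3.1 allows the nominal range to be extended "up to a maximum dosage of 1000 mg per day".
- Section 3.1 and SAP Section 2.1 say enrolment depends on "the number of dose levels required to identify the MTD or Recommended Phase 2 Dose (RP2D) if the MTD is not reached".

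**The concern.** Every limit that applies to the MTD label is an upper one. Nothing in the working rule separates a dose that is the MTD because the next dose was too toxic from a dose that is merely the last one opened. The plan allows escalation to stop for reasons other than toxicity, so the second case is foreseeable. Section 1.5.1 projects the pharmacologically active dose at 500 mg QD or 200 mg BID, so target coverage could be reached before any dose-limiting toxicity.

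Taken literally, the rule treats the MTD as reached once any tested dose has a DLT rate of 32.5% or less. The not-reached outcome would then apply only if every tested dose exceeded 32.5%, which is the opposite of its evident meaning. Determining the MTD or RP2D is a Part 1 primary objective. A report that followed Section 3.3 exactly could state a tolerability limit that was never observed.

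**Working it through.** **Inputs.** Prior Beta(0.5, 0.5) and intervals (0, 0.225), (0.225, 0.325), (0.325, 1) from Section 9.2.1; decisions from Table 2; the 32.5% limit from Section 3.3; 6 to 12 patients from Section 3.1.1.

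**Step 1: reproduce Table 2 for the three examples.** With x DLTs in n patients the posterior is Beta(0.5+x, 0.5+n−x), with distribution function F. The unit probability mass of an interval (a, b) is [F(b) − F(a)]/(b − a), and the largest of the three gives the decision. For 0/6, the underdosing value is 0.926/0.225 ≈ 4.115.

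| DLTs | Observed rate | P(p<0.225) | P(0.225–0.325) | P(p>0.325) | UPM E / S / D | Table 2 |
|---|---|---|---|---|---|---|
| 0/6 | 0% | 0.926 | 0.048 | 0.0265 | 4.115 / 0.475 / 0.039 | E |
| 1/6 | 16.7% | 0.597 | 0.192 | 0.2117 | 2.651 / 1.918 / 0.314 | E |
| 0/12 | 0% | 0.988 | 0.011 | 0.0019 | 4.389 / 0.105 / 0.003 | E |

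(UPMs use unrounded probabilities.) All three agree with Table 2. Across the table, 69 of 73 cells reproduce if Unacceptable is taken as a De-escalate result with P(p>0.275)>0.95; that cutoff is an assumption. The four that differ (4/9, 4/10, 5/11, 5/12: computed Stay, printed De-escalate) all exceed 33% and do not affect this point.

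**Step 2: apply Section 3.3.** The rates 0%, 16.7% and 0% are all at or below 32.5%. If the dose is the highest tested, the rule calls each the MTD.

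**Step 3: count the cells.** For n = 6 to 12, the Table 2 cells with x/n ≤ 0.325 number 2+3+3+3+4+4+4 = 23.

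- Escalate: 0/6 to 0/12 (7), 1/6 to 1/12 (7), 2/11 and 2/12, giving 16.
- Stay: 2/7, 2/8, 2/9, 2/10, 3/10, 3/11, 3/12, giving 7.
- De-escalate or Unacceptable: none.

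Only 5 of the 23 (2/7, 2/8, 3/10, 3/11, 3/12) fall inside 22.5–32.5%. At n = 6 both qualifying outcomes, 0/6 and 1/6, are Escalate. These are counts of cells, not probabilities.

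**Step 4: chance at a single top dose.** Table 2 gives Escalate for at most 1 DLT in 6 or at most 2 in 12. At a true rate of 10% and n = 6 the chance is 0.9^6 + 6(0.1)(0.9^5) = 0.531 + 0.354 = 0.886; at n = 12 it is 0.889. At a true 5% the values are 0.967 and 0.980.

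**Step 5: chance over a whole trial.** The documents give no DLT curve, so three were assumed. Settings: QD levels 125/250/500/750/1000 mg, Table 2 decisions, at most 12 patients per dose, escalation ending at 1000 mg, 20,000 trials per setting. Entries are the proportion of trials in which Section 3.3 labels the top opened dose as MTD while Table 2 says Escalate.

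| Assumed true rates (%) | Cohort 2, final n 6 / 12 | Cohort 3, 6 / 12 | Cohort 4, 6 / 12 |
|---|---|---|---|
| 2-4-6-8-10 | 0.895 / 0.848 | 0.867 / 0.826 | 0.846 / 0.830 |
| 5-10-15-20-25 | 0.398 / 0.262 | 0.342 / 0.226 | 0.234 / 0.194 |
| 5-10-20-30-45 | 0.081 / 0.019 | 0.061 / 0.015 | 0.020 / 0.010 |

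If the trial may also stop at a lower dose that has the final n, a Stay decision and a rate of 32.5% or less, the ranges become 65–84%, 12–32% and 1–7%.

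**The case against.** The best defence is that Section 3.3 should be read whole. Its earlier sentences give the 27.5% target and a two-sided interval. The opening words of the rule suggest a tie-break towards the safer dose, and the sentence closes by pointing to Table 2. The plan also foresees an unreached MTD, and the objective is met by an MTD or an RP2D. A sensible team would report the MTD as not reached after 0/6 at the top dose.

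That may well be the intent, but no such limit is written. Table 2 holds cohort decisions and no MTD rule, and in the Escalate cells it contradicts the label. No text says when the not-reached outcome applies.

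The objection to the size has force. The 83–90% figure needs a very well-tolerated drug and a hard stop at 1000 mg QD. Table 1 does not clearly stop there: QD level 6 is still to be determined, and the BID column runs to 1000 mg twice daily. The simulation leaves BID out.

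A reader might also infer that the defect is the missing lower bound. It is not. A dose with few DLTs just below a rejected dose is a legitimate MTD, and a 22.5% floor would wrongly exclude it. The gap is the missing condition for a top dose that has not been shown to be at its limit.

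**Conclusion.** The point holds as a labelling error in a stated rule for a primary objective. It arises only when the highest dose opened meets the 32.5% limit and its final Table 2 decision is Escalate. If the top dose exceeds 32.5%, the rule correctly steps down.

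That 0/6, 1/6 and 0/12 are mislabelled follows from the documents alone. How often this happens does not: it depends on the unknown DLT curve and on where escalation stops. Under the assumed curves it is common if the drug is well tolerated and rare if a toxic dose is reached. No single percentage should be quoted as the trial's risk.

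A reader might infer that patients are put at risk, that a wrong dose is forced into Part 2, or that the range extension is blocked. The documents support none of these. Table 2 still governs dosing. Section 3.5 says the MTD usually becomes the RP2D, bases the RP2D on the Phase 1 results and allows a lower dose. The extension in Section 3.1 turns on the MTD or RP2D not being reached together with sub-optimal coverage, so the label does not necessarily stop it. Section 9.6.1 and SAP Section 8.2.4.1 list DLTs by dose level, so the counts would stand beside the label.

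**What to change.** Replace the working rule in Section 3.3, with matching text in SAP Section 8.1, by:

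> If the highest dose tested has a DLT rate ≤32.5% and its final Table 2 decision is E, no MTD is declared; the result is reported as MTD not reached, with the maximum administered dose and its DLT count. Otherwise the MTD is the highest tested dose with DLT rate ≤32.5%.

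At a top dose, the 16 Escalate cells in step 3 change from MTD to not reached, and the 7 Stay cells keep the MTD label. A low-rate dose below a rejected one also keeps it. The wording removes the mislabel by construction, so no simulation is needed to show that.

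Table 2, dosing and enrolment are unchanged; the cost is two sentences in each document. The downside is that the report may have to state that no MTD was reached, in just the trials counted in step 5. The protocol already anticipates that outcome.

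A minimum of six evaluable patients for a declared MTD is optional and not needed to correct the error. A stricter definition combining that minimum with a formally rejected higher dose, or a Stay decision at the dose itself, returned no MTD in 10–15% of simulated trials on the 5–45% curve, against 1–8% here. Most of that difference came from the six-patient minimum.

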**3.4. Late Onset Toxicity and Toxicities Observed in the Expansion Phase**

Adverse events that meet the same grading criteria as the DLT criteria listed above occurring after the DLT observation period will lead Pfizer to immediately schedule a meeting with the investigators to review the details of the potential late onset toxicity and determine if the enrollment has to be held for this dose level or if a dose reduction should be implemented for all ongoing patients. Late onset toxicities meeting the definition of a DLT will be used in the evaluation of the MTD.

In addition, adverse events that meet the same grading criteria as the DLT criteria listed above occurring in the expansion phase (Part 2) will prompt Pfizer to immediately schedule a meeting with the investigators to review the details of the toxicity and determine the necessary action to be implemented for all patients.

### **3.5. Recommended Phase 2 Dose (RP2D) Definition**

The RP2D is the dose chosen for further study based on Phase 1 study results. If the MTD proves to be clinically feasible for long-term administration in a reasonable number of patients, then this dose usually becomes the RP2D. Further experience with the MTD may result in a RP2D dose lower than the MTD.

## **4. PATIENT SELECTION**

This study can fulfill its objectives only if appropriate patients are enrolled. The following eligibility criteria are designed to select patients for whom participation in the study is considered appropriate. All relevant medical and non-medical conditions should be taken into consideration when deciding whether a particular patient is suitable for this protocol.

### **4.1. Inclusion Criteria**

Patient eligibility should be reviewed and documented by an appropriate member of the investigator's study team before patients are included in the study.

Patients must meet all of the following inclusion criteria to be eligible for enrollment into the study:

1. Pathologically documented and definitively diagnosed recurrent WHO Grade IV GBM.
2. Pathologically documented and definitively diagnosed recurrent WHO Grade III anaplastic gliomas (including anaplastic astrocytoma, anaplastic oligodendroglioma, anaplastic oligoastrocytoma and mixed gliomas) – Part 1 only.
3. Access to archived formalin fixed paraffin embedded material from the initial diagnosis or subsequent relapse of Grade IV GBM or Grade III anaplastic glioma that is of diagnostic quality and representative of their diagnosed malignancy available for submission to the sponsor. If archival tissue is not available, the patient must consent to surgical intervention to acquire tumor tissue at screening.
4. For patients with Grade IV GBM, recurrent disease (confirmed by MRI and evaluable by Macdonald criteria) at the time of first or second recurrence or progression following prior definitive therapy(s) such as surgery with adjuvant radiation therapy and/or chemotherapy. For patients with Grade III anaplastic glioma, recurrent disease (confirmed by MRI and evaluable by Macdonald criteria) at the time of at least a first recurrence but no more than a fourth recurrence or progression following prior definitive therapy(s).
5. Must have recovered to Grade 0 or 1 or pre-treatment baseline from clinically significant toxic effects of prior therapy (including but not limited to exceptions of alopecia, laboratory values listed per inclusion criteria, and lymphopenia which is common after therapy with temozolomide).

6. Must have stable dosing of corticosteroid treatment for at least 7 days prior to registration and are neurologically stable.
7. Must have recovered from the acute effects of radiation therapy or surgery or systemic treatment prior to study entry.
8. Age  $\geq 18$  years.
9. Karnofsky performance score  $\geq 70\%$ .
10. Have received no more than two prior lines of therapy.
11. Adequate Hematologic Function, including:
  - a. Absolute Neutrophil Count (ANC)  $\geq 1,500/\text{mm}^3$  or  $\geq 1.5 \times 10^9/\text{L}$ ;
  - b. Platelets  $\geq 100,000/\text{mm}^3$  or  $\geq 100 \times 10^9/\text{L}$ ;
  - c. Hemoglobin  $\geq 9$  g/dL.
  - d. Prothrombin time (PT) or partial thromboplastin time (PTT)  $< 1.5$  x upper limit of normal (ULN).
12. Adequate Renal Function, including:
  - a. Estimated creatinine clearance  $\geq 60$  mL/min as calculated using the Cockcroft-Gault calculator. A 24-hour urine collection is not required but should be used to confirm estimated creatinine clearance if a urine collection is obtained as part of standard of care.
13. Adequate Liver Function, including:
  - a. Total serum bilirubin  $\leq 1.0$  x ULN unless the patient has documented Gilbert syndrome or extrahepatic source by increased indirect bilirubin function;
  - b. Aspartate and Alanine transaminase (AST and ALT)  $\leq 1.5$  x ULN ( $\leq 3$  x ULN for patients on chronic anticonvulsive therapies known to increase transaminases)
  - c. Alkaline phosphatase  $\leq 1.5$  x ULN; ( $\leq 3$  x ULN for patients on chronic anticonvulsive therapies known to increase transaminases)
14. Serum or urine pregnancy test (for females of childbearing potential) negative at screening.
15. Male patients able to father children and female patients of childbearing potential and at risk for pregnancy must agree to use two highly effective methods of contraception throughout the study and for at least 28 days after the last dose of assigned treatment.

Female patients who are not of childbearing potential (ie, meet at least one of the following criteria):

- Have undergone a documented hysterectomy and/or bilateral oophorectomy;
  - Have medically confirmed ovarian failure; or
  - Achieved postmenopausal status, defined as follows: cessation of regular menses for at least 12 consecutive months with no alternative pathological or physiological cause and have a serum follicle-stimulating hormone (FSH) level within the laboratory's reference range for postmenopausal women.
16. Evidence of a personally signed and dated informed consent document indicating that the patient has been informed of all pertinent aspects of the study.
17. Patients who are willing and able to comply with scheduled visits, treatment plans, laboratory tests and other procedures.

#### **4.2. Exclusion Criteria**

Patients with any of the following characteristics/conditions will not be included in the study:

1. History of CNS bleeding as defined by stroke or intraocular bleed (including embolic stroke) within 6 months before registration.
2. Evidence of acute intracranial / intratumoral hemorrhage, except for patients with stable Grade 1 hemorrhage.
3. Peripheral sensory neuropathy  $\geq$  Grade 2.
4. Requires treatment with high dose systemic corticosteroids defined as dexamethasone (or equivalent)  $>2$  mg/day or bioequivalent for at least 3 consecutive days within 2 weeks of registration.
5. Previous high-dose chemotherapy requiring stem cell rescue.
6. Previous anti-angiogenic or anti-vascular endothelial growth factor (VEGF) targeted agents (eg, bevacizumab, cediranib, aflibercept, vandetanib, XL-184, sunitinib, etc.) within 12 months of registration. In addition, patients who experienced significant bleeding during bevacizumab treatment will also be excluded.
7. Surgical resection within 4 weeks of registration.
8. Completion of radiation therapy within 12 weeks of registration unless there is a new area of enhancement consistent with recurrent tumor outside the radiation field or there is unequivocal histologic confirmation of tumor progression.

9. Cytotoxic therapy within 4 weeks (except 6 weeks for nitrosoureas), investigational agent within 5 half-lives, antibody within 6 weeks or any other anti-tumor therapies within 4 weeks (or 5 half-lives, whichever is shorter) of registration.
10. History of suicidal ideation within 12 months of registration. Patients who have a history of suicidal ideation within 12 months of registration can be included if a risk assessment by a qualified mental healthcare professional determines the patient is deemed acceptable for inclusion.
11. Life expectancy of less than 3 months in the opinion of the investigator.
12. Prior treatment with a compound of the same mechanism.
13. Active and clinically significant bacterial, fungal, or viral infection, including hepatitis B (HBV), hepatitis C (HCV), known human immunodeficiency virus (HIV) or acquired immunodeficiency syndrome (AIDS)-related illness.
14. Any of the following in the previous 6 months: myocardial infarction, symptomatic congestive heart failure (New York Heart Association > class II), unstable angina, or uncontrolled hypertension (defined as systolic >160 mmHg or diastolic >100 mmHg).
15. History of other malignancies, except: adequately treated non-melanoma skin cancer, curatively treated in-situ cancer, or other solid tumors curatively treated with no evidence of disease for  $\geq 2$  years.
16. Active inflammatory gastrointestinal disease, chronic diarrhea, known diverticular disease or previous gastric resection or lap-band. Gastroesophageal reflux disease under treatment with proton pump inhibitors is allowed.
17. Current use or anticipated need for food or drugs that are known strong CYP1A2 inhibitors, including their administration within 10 days prior to the first PF-06840003 dose (such as, but not limited to: Strong CYP1A2 Inhibitors: fluvoxamine, ciprofloxacin, clinafloxacin, enoxacin, oltipraz, propranolol, rofecoxib, thiabendazole, and zafirlukast).
18. Current use or anticipated need for food or drugs that are known strong CYP1A2 inducers, including their administration within 10 days prior to the first PF-06840003 dose (ie, Strong CYP1A2 Inducers: tobacco (including cigarettes and products containing tobacco)).
19. Patients with known malabsorption syndrome or other condition that may impair absorption of study medication.
20. Severe acute or chronic medical or psychiatric condition, including recent laboratory abnormality that may increase the risk associated with study participation or investigational product administration or may interfere with the interpretation of study results and, in the judgment of the investigator, would make the patient inappropriate for entry into this study.

21. Patients who are investigational site staff members directly involved in the conduct of the study and their family members, site staff members otherwise supervised by the investigator, or patients who are Pfizer employees directly involved in the conduct of the study.

22. Pregnant female patients; breastfeeding female patients.

